10.1.5 Reporting of study treatment errors including misuse/abuse

Medication errors are unintentional errors in the prescribing, dispensing, administration or monitoring of a medicine while under the control of a healthcare professional, subject or consumer (EMA definition).

Misuse refers to situations where the medicinal product is intentionally and inappropriately used not in accordance with the protocol.

Abuse corresponds to the persistent or sporadic, intentional excessive use of a medicinal product, which is accompanied by harmful physical or psychological effects.

Study treatment errors and uses outside of what is foreseen in the protocol will be collected in the DAR eCRF irrespective of whether or not associated with an AE/SAE and reported to Safety only if associated with an SAE. Misuse or abuse will be collected and reported in the safety database irrespective of it being associated with an AE/SAE within 24 hours of Investigator's awareness.

Table 10-2 Guidance for capturing the study treatment errors including misuse/abuse

Treatment error type	Document in Dose Administration (DAR) eCRF (Yes/No)	Document in AE eCRF	Complete SAE form
Unintentional study treatment error	Yes	Only if associated with an AE	Only if associated with an SAE
Misuse/Abuse	Yes	Yes	Yes, even if not associated with a SAE

For more information on AE and SAE definition and reporting requirements, please see the, respective sections.

10.2 Additional Safety Monitoring

Not applicable

10.2.1 Liver safety monitoring

Please, refer to [Section 6.5.1.3.2](#).

All follow-up information, and the procedures performed must be recorded as appropriate in the CRF.

10.2.2 Renal safety monitoring

Please refer to [Section 6.5.1.3.3](#).

All follow-up information, and the procedures performed must be recorded as appropriate in the CRF.

10.2.3 Data Monitoring Committee

This study will include a DMC that will function independently of all other individuals associated with the conduct of this clinical trial, including the site investigators participating in

the study. The DMC will assess at defined intervals the progress of the clinical trial, safety data, and critical efficacy variables and recommend whether to continue, modify or terminate the trial. The DMC will be informed and convened quickly in the event of unexpected results that raise concerns to permit DMC evaluation and input. An IA for futility of the primary endpoint will be conducted when the first 200 subjects dosed have been followed for 6 months (either completed 6 months of treatment or discontinued treatment earlier) (see [Section 12.7](#) and the DMC charter for details). At the time of this IA, the futility of a secondary efficacy endpoint RFS will also be assessed.

Responsibilities of the DMC and communication flow between the DMC and Novartis will be described in the DMC charter document. It is expected that the DMC will consist at a minimum of two physicians with appropriate disease area qualifications and one statistician.

10.2.4 Steering Committee

The steering committee will be established comprising investigators participating in the trial, i.e. not being members of the DMC and Novartis representatives from the Clinical Trial Team.

The SC will ensure transparent management of the study according to the protocol through recommending and approving modifications as circumstances require. The SC will review protocol amendments as appropriate. Together with the clinical trial team, the SC will also develop recommendations for publications of study results including authorship rules. The details of the membership and role of the Steering Committee will be defined in a Steering Committee charter.

11 Data Collection and Database Management

11.1 Data collection

The designated investigator staff will enter the data required by the protocol into the Electronic Case Report Forms (eCRF). The eCRFs have been built using fully validated secure web-enabled software that conforms to 21 CFR Part 11 requirements, Investigator site staff will not be given access to the EDC system until they have been trained. Automatic validation programs check for data discrepancies in the eCRFs, allow modification and/or verification of the entered data by the investigator staff.

The Principal investigator is responsible for assuring that the data (recorded on CRFs) (entered into eCRF) is complete, accurate, and that entry and updates are performed in a timely manner. The Investigator must certify that the data entered are complete and accurate.

After final database lock, the investigator will receive copies of the subject data for archiving at the investigational site.

All data should be recorded, handled and stored in a way that allows its accurate reporting, interpretation and verification.

11.2 Database management and quality control

Novartis personnel (or designated CRO) will review the data entered by investigational staff for completeness and accuracy. Electronic data queries stating the nature of the problem and

requesting clarification will be created for discrepancies and missing values and sent to the investigational site via the EDC system. Designated investigator site staff are required to respond promptly to queries and to make any necessary changes to the data.

Concomitant treatments and prior medications entered into the database will be coded using the WHO Drug Reference List, which employs the Anatomical Therapeutic Chemical classification system. Medical history/current medical conditions and adverse events will be coded using the Medical dictionary for regulatory activities (MedDRA) terminology.

Data about all study treatment (s) dispensed to the subject and all dosage changes will be tracked using an Interactive Response Technology (IRT) for clinically supplied drug. The system will be supplied by a vendor, who will also manage the database. The data will be sent electronically to Novartis (or a designated CRO) at specific timelines. IRT will not be utilized to track study drug that is sourced as local commercial supply; this information will be recorded on local study drug accountability logs.

Once all the necessary actions have been completed and the database has been declared to be complete and accurate, it will be locked. Any changes to the database after that time can only be made after written agreement by Novartis development management.

After database lock, the investigator will receive a CD-ROM or paper copies of the subject data for archiving at the investigational site.

11.3 Site monitoring

Before study initiation, at a site initiation visit or at an investigator's meeting, a Novartis representative will review the protocol and data capture requirements (eCRFs) with the investigators and their staff. During the study, Novartis employs several methods of ensuring protocol and GCP compliance and the quality/integrity of the sites' data. The field monitor will visit the site to check the completeness of subject records, the accuracy of data capture / data entry, the adherence to the protocol and to Good Clinical Practice, the progress of enrollment, and to ensure that study treatment is being stored, dispensed, and accounted for according to specifications. Key study personnel must be available to assist the field monitor during these visits. Continuous remote monitoring of each site's data may be performed by a centralized Novartis. Additionally, a central analytics organization may analyze data & identify risks & trends for site operational parameters, and provide reports to Novartis clinical teams to assist with trial oversight.

The investigator must maintain source documents for each subject in the study, consisting of case and visit notes (hospital or clinic medical records) containing demographic and medical information, laboratory data, electrocardiograms, and the results of any other tests or assessments. All information on CRFs must be traceable to these source documents in the subject's file. The investigator must also keep the original informed consent form signed by the subject (a signed copy is given to the subject).

The investigator must give the monitor access to all relevant source documents to confirm their consistency with the data capture and/or data entry. Novartis monitoring standards require full verification for the presence of informed consent, adherence to the inclusion/exclusion criteria, documentation of SAEs, and of data that will be used for all primary variables. Additional checks of the consistency of the source data with the CRFs are performed according to the

study-specific monitoring plan. No information in source documents about the identity of the subjects will be disclosed.

12 Data analysis and statistical methods

One IA for fertility is planned for the study when approximately the first 200 subjects dosed have been followed for 6 months (either completed 6 months of treatment or discontinued treatment earlier.) Primary statistical analysis will be performed 12 months after LPFV. Final analysis of the study will be performed at the end of the study defined as 24 months after LPFV.

The data will be summarized with respect to demographic and baseline characteristics, and safety observations and efficacy measurements. Categorical data will be presented as frequencies and percentages. For continuous data, mean, standard deviation, median, minimum, and maximum will be presented.

12.1 Analysis sets

The Full Analysis Set (FAS) and Safety Set are defined in the same way and comprise all subjects who received at least one dose of study treatment.

The Safety Set includes all subjects who received at least one dose of study treatment.

12.2 Subject demographics and other baseline characteristics

Summary statistics of subject demographics and baseline characteristics will be provided using FAS. Categorical data will be presented as frequencies and percentages. For continuous data, mean, standard deviation, median, minimum, and maximum will be presented.

Relevant medical histories and current medical at baseline will be summarized by system organ class and preferred term.

12.3 Treatments

The safety set will be used for the analyses below. Categorical data will be summarized as frequencies and percentages. For continuous data, mean, standard deviation, median, 25th and 75th percentiles, minimum, and maximum will be presented.

The duration of exposure in dabrafenib and trametinib and their dose intensity (computed as the ratio of actual cumulative dose received and actual duration of exposure) will be summarized by means of descriptive statistics using the safety set.

The number of subjects with dose adjustments (reductions, interruption, or permanent discontinuation) and the reasons will be summarized and all dosing data will be listed.

Concomitant medications and significant non-drug therapies prior to and after the start of the study treatment will be listed and summarized according to the Anatomical Therapeutic Chemical (ATC) classification system.

12.4 Analysis of the primary endpoint(s)

To assess whether an adapted AE-management algorithm for pyrexia will reduce the incidence of grade 3/4 pyrexia, hospitalization due to pyrexia, or permanent treatment discontinuation due to pyrexia compared to historical control.

12.4.1 Definition of primary endpoint(s)

The primary endpoint is defined as the composite rate of grade 3/4 pyrexia, hospitalization due to pyrexia or permanent treatment discontinuation due to pyrexia up to 12 months of therapy among overall treated subjects.

The rate of this composite endpoint is calculated as the total number of subjects experiencing at least one of the three components of the composite endpoint (i.e., grade 3/4 pyrexia, hospitalization due to pyrexia, or permanent treatment discontinuation due to pyrexia), divided by the total number of subjects in the FAS. The composite endpoint is assessed over a treatment period of 12 months.

12.4.2 Statistical model, hypothesis, and method of analysis

The primary analysis will be based on the calculation of the observed pyrexia event rate up to 12 months of therapy (primary endpoint) using the FAS. The observed pyrexia event rate will be summarized using descriptive statistics (N, %) along with its two-sided exact 95% confidence interval (Clopper and Pearson 1934).

In the COMBI-AD study, 87 out of 435 subjects in the treatment arm (20%) developed either grade 3/4 pyrexia or hospitalization due to pyrexia or discontinued due to pyrexia. This rate of 20% will be used as the historical control rate for the assessment of pyrexia management algorithm in this study.

Evidence of treatment effect (improvement in pyrexia event rate using the AE-management algorithm) will be concluded, if the upper bound of the two-sided 95% confidence interval is less than 20%.

The exact 95% confidence intervals for various observed event rates at the primary analysis are shown in [Table 12-1](#). If 100 (16.7%) out of 600 subjects are observed with pyrexia event, then the upper bound of the 95% confidence interval will be less than 20%.

Table 12-1 Exact 95% CI for different observed event rates at primary analysis

N	r	Pyrexia event rate (%)	95% exact CI (%)*
600	100	16.7	13.8 – 19.9
600	101	16.8	13.9 – 20.1
600	102	17.0	14.1 – 20.2
600	103	17.2	14.2 – 20.4
600	104	17.3	14.4 – 20.6
600	105	17.5	14.5 – 20.8

N: Total numbers of subjects;

r: Number of subjects with pyrexia events at primary analysis

* Clopper and Pearson (1934)

In addition, the probability that the pyrexia even rate is below the threshold of 20% will be calculated from the posterior distribution. For illustration, as shown in [Table 12-2](#), if 104 out of 600 subjects are observed with pyrexia events at primary analysis, then the posterior probability of observing an event rate of < 20% is 0.954 (probability \geq 0.95).

Table 12-2 Posterior probability for a positive effect at primary analysis

N	r	Pyrexia event rate (%)	Posterior* Pr (event rate<20% data)
600	100	16.7	0.983
600	101	16.8	0.977
600	102	17.0	0.971
600	103	17.2	0.963
600	104	17.3	0.954
600	105	17.5	0.943
600	110	18.3	0.854
600	115	19.2	0.703
600	120	20.0	0.508
600	125	20.8	0.313
600	130	21.7	0.161
600	135	22.5	0.068

N: Total numbers of subjects;

r: Number of subjects with pyrexia events at primary analysis

* A diffuse (highly non-informative) prior distribution of the composite rate with a skeptical expectation of 20%, namely Beta (0.25, 1) is assumed.

12.4.3 Handling of missing values/censoring/discontinuations

No missing data imputation rule will be applied to the primary analysis. For the primary endpoint, subjects who discontinued prematurely prior to 12 months without pyrexia will be counted as no event.

12.5 Analysis of secondary endpoints

12.5.1 Efficacy endpoints

The secondary endpoints are the RFS and OS rates at 12 and 24 months.

RFS is defined as the time from the date of first dose of the study medication to the date of disease recurrence or death due to any cause. Treatment emergent malignancies other than second melanomas will not be considered as events. RFS will be censored if no RFS event is observed before the first to occur between: (i) the analysis cut-off date, and (ii) the date when a new anti-cancer therapy is started. The censoring date will be the date of the last adequate tumor assessment prior to cut-off/start of new anti-cancer therapy.

OS is defined as the time from date of the first dose of study medication to date of death due to any cause. If a subject is not known to have died, then OS will be censored at the latest date the subject was known to be alive (on or before the cut-off date).

RFS and OS will be analyzed descriptively in the FAS population. The RFS and OS distribution will be estimated using the Kaplan-Meier method, and the Kaplan-Meier curves, medians and 95% confidence intervals of the medians will be presented.

12.5.2 Safety endpoints

Other secondary objectives related to safety include:

- To evaluate overall AE rate leading to permanent treatment discontinuation by 12 months
- Frequency, number of episodes, duration, AE management (including concomitant medications and study treatment modifications) due to pyrexia
- To evaluate overall safety (AEs and SAEs)

For all safety analyses, the safety set will be used.

The overall observation period will be divided into three mutually exclusive segments:

1. pre-treatment period: from day of subject's informed consent to the day before first dose of study medication
2. on-treatment period: from day of first dose of study medication to 30 days after last dose of study medication
3. post-treatment period: starting at day 30+1 after last dose of study medication.

Adverse events

Summary tables for adverse events (AEs) will include only AEs that started or worsened during the on-treatment period, the *treatment-emergent* AEs.

The incidence of treatment-emergent adverse events (new or worsening from baseline) will be summarized by system organ class and or preferred term, severity (based on CTCAE grades), type of adverse event, relation to study treatment.

Serious adverse events, non-serious adverse *events* and adverse events of special interest (AESI) during the on-treatment period will be tabulated.

All deaths (on-treatment and post-treatment) will be summarized.

All AEs, deaths and serious adverse events (including those from the pre and post-treatment periods) will be listed and those collected during the pre-treatment and post-treatment period will be flagged.

The proportion of subjects in the study, who have permanently discontinued treatment due to any AE, will be estimated, along with 95% confidence intervals using Clopper Pearson exact method.

Vital signs

All vital signs data will be listed by treatment group, subject, and visit/time and if ranges are available, abnormalities will be flagged. Summary statistics will be provided by treatment and visit/time.

Clinical laboratory evaluations

Grading of laboratory values will be assigned programmatically as per NCI Common Terminology Criteria for Adverse Events (CTCAE) version 4.03. The calculation of CTCAE grades will be based on the observed laboratory values only, clinical assessments will not be taken into account.

CTCAE Grade 0 will be assigned for all non-missing values not graded as 1 or higher. Grade 5 will not be used.

For laboratory tests where grades are not defined by CTCAE v 4.03, results will be categorized as low/normal/high based on laboratory normal ranges.

The following summaries will be generated separately for hematology, and biochemistry tests:

- Listing of all laboratory data with values flagged to show the corresponding CTCAE v4.03 grades if applicable and the classifications relative to the laboratory normal ranges

For laboratory tests where grades are defined by CTCAE v4.03

- Worst post-baseline CTCAE grade (regardless of the baseline status). Each subject will be counted only once for the worst grade observed post-baseline.
- Shift tables using CTCAE v4.03 grades to compare baseline to the worst on-treatment value

For laboratory tests where grades are not defined by CTCAE v4.03,

- Shift tables using the low/normal/high/ (low and high) classification to compare baseline to the worst on-treatment value.

12.5.3 Patient reported outcomes

Changes in HRQOL from baseline will be assessed using the FACT-M questionnaire. The summary table of change in HRQOL from baseline will be presented by using the FAS.

12.6 Analysis of exploratory endpoints

Not applicable

12.7 Interim analyses

One IA for futility of the primary endpoint is planned for the study when approximately the first 200 subjects dosed have been followed for 6 months (either completed 6 months of treatment or discontinued treatment earlier.) At the time of this IA, the futility of a secondary efficacy endpoint RFS will also be assessed. This analysis will allow assessing the impact of the adapted pyrexia AE-management algorithm on both the pyrexia event rate and the RFS rate at 6 months. The DMC will review the IA results and make a recommendation using the scenarios provided below. Any decision to stop or continue the pyrexia management algorithm will be made based on all data available at the IA cut-off taking the futility analysis into account.

From the COMBI-AD study that used the approved pyrexia management algorithm, the pyrexia event rate (composite rate of grade 3/4 pyrexia, hospitalization due to pyrexia, or permanent treatment discontinuation due to pyrexia) at 12 month observed for dabrafenib + trametinib (N=435) was: 20% with 95% CI (16%, 24%). Under the new pyrexia treatment algorithm, an observed primary endpoint rate of at least 20% may indicate lack of improvement of the new algorithm. Assessment of futility for primary endpoint will be based on the calculated Bayesian predictive probabilities of the event that observed pyrexia event rate will be 20% or more in the FAS, if the study is continued beyond the interim (i.e. till the primary analysis).

The pyrexia event rate is assumed to be binary and the number of subjects with pyrexia events is assumed to follow a binomial distribution. Suppose the prior belief regarding the probability of event rate (π) is that it has a beta distribution with parameters a_0 and b_0 . If there are x events out of n subjects, then the posterior distribution for π is beta with parameters $a_1 = a_0 + x$ and $b_1 = b_0 + n - x$. Now let Y represent the number of subjects with pyrexia events from m future observations, then the (posterior) predictive distribution of Y conditional on the observed data at the interim (x events out of n subjects) is a beta-binomial distribution described by

$$p(Y = y|x, n) = \binom{m}{y} \frac{B(a_0+x+y, b_0+n-x+m-y)}{B(a_0+x, b_0+n-x)}$$

where $B(a, b)$ is the beta function.

A diffuse (highly non-informative) prior distribution of the composite rate with a skeptical expectation of 20%, namely Beta (0.25, 1) is assumed.

Under these assumptions, the DMC will be provided the predictive probability of observing pyrexia event rate of $\geq 20\%$, a criterion that may trigger consideration for stopping the study taking account of all available data and not just the pyrexia event rate data required for determination of futility.

Table 12-3 shows the predictive probabilities of observing pyrexia event rate $\geq 20\%$ ($n=200$) under different interim results. For illustration, with 200 subjects at IA, if the observed pyrexia event rate is 22%, the probability of observing the pyrexia event rate $\geq 20\%$ at primary analysis is $> 80\%$. The DMC might interpret this scenario as an outcome where stopping the study for futility may be a sensible option. If the observed pyrexia event rate is 18% at IA, the probability of observing the pyrexia event rate $\geq 20\%$ at primary analysis is $< 20\%$.

Table 12-3 Predictive probability of observing composite pyrexia event rate greater or equal 20% (n=200) in the safety set at primary analysis (600 subjects) under different interim results

Observed rate at IA (n=200)		Predictive probability of observing pyrexia event rate \geq 20% at primary analysis*
# of subjects with pyrexia events	%	
30	15	0.0135
32	16	0.0392
34	17	0.0943
36	18	0.1913
38	19	0.3318
40	20	0.5000
42	21	0.6673
44	22	0.8058
46	23	0.9015
48	24	0.9569
50	25	0.9838
52	26	0.9948
54	27	0.9986
56	28	0.9997
58	29	0.9999
60	30	1.0000

*prior distribution Beta (0.25, 1) is assumed.

At the time of this IA, the DMC will also be provided with interim results for the secondary endpoint RFS. Similar to the futility analysis for the primary endpoint, Bayesian predictive probabilities of the RFS rate will be provided.

From the COMBI-AD study, the Kaplan-Meier estimated RFS rate at 12 month for control group and treatment group were: 56% with 95% CI (51%, 61%) and 88% with 95% CI (85%, 91%), respectively. We consider the futility threshold of 12-month RFS rate of 61%, which is the upper bound 95% CI of control group, and calculate the predictive probability (PP) as follows:

$$PP = \text{Prob. [Observed 12 month RFS rate} \geq 61\% \mid x, n; x \text{ successes among } n \text{ subjects}]$$

The DMC will be provided the predictive probability of observing RFS of $\geq 61\%$, a criterion that may trigger consideration for stopping the study taking account of all available data and not just the RFS data required for determination of futility.

Table 12-4 shows the predictive probabilities of observing RFS rate $\geq 61\%$ (n=200) under different interim results. For illustration, with 200 subjects at IA, if the observed RFS rate at 6-month is 65%, the probability of observing the RFS rate $\geq 61\%$ at the primary analysis at 12 months is $> 90\%$. If the observed RFS rate is 57%, the probability of observing the RFS rate $\geq 61\%$ at the primary analysis is $< 10\%$.

Table 12-4 Predictive probability of observing RFS rate greater or equal 61% (n=200) at the secondary analysis (600 subjects)

Observed rate at IA (n=200)	
-----------------------------	--

# of relapse free	%	Predictive probability of observing RFS rate \geq 61% at secondary analysis*
110	55	0.0163
112	56	0.0371
114	57	0.0760
116	58	0.1403
120	60	0.3550
122	61	0.4930
124	62	0.6321
128	64	0.8529
130	65	0.9201

*prior distribution Beta (0.37, 1) is assumed.

Subject enrollment will not be stopped for the IA. According to enrollment expectation, approximately 570 subjects are planned to be included in the study at the time of the IA cutoff.

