Data analysis	
 • The data will be summarized with respect to demographic, baseline characteristics, safety observations and efficacy measurements. Categorical data will be presented as frequencies and percentages. For continuous data, mean, standard deviation, median, minimum, and maximum will be presented. • The primary analysis will be based on the calculation of the observed pyrexia event rate (composite rate of grade 3/4 pyrexia, hospitalization due to pyrexia or permanent treatment discontinuation due to pyrexia) and its 95% two-sided exact confidence interval (Clopper and Pearson 1934) up to 12 months of therapy. • The study will meet its primary objective if the upper bound of the two-sided 95% CI is less than 20%. • The secondary endpoints RFS and OS distribution will be estimated by using Kaplan-Meier approach. • One IA for futility of the primary endpoint and the secondary endpoint RFS is planned for the study when approximately the first 200 subjects dosed have been followed for 6 months (either completed 6 months of treatment or discontinued treatment earlier.) • The sample size of 600 subjects has been chosen so that the study operating characteristics comply with the requirement to have a high probability (> 95%) to declare futility at IA if the true 12-month pyrexia event rate is $\geq 20\%$.
Key words	dabrafenib, trametinib, adjuvant, melanoma, combination treatment, pyrexia

Amendment 2 (12-Mar-2019)

As of 12-Mar-2019, 86 sites have been initiated, 311 subjects have enrolled into the study, and 234 subjects have started treatment in the study.

Amendment rationale

The primary purpose of this protocol amendment is to implement clinically relevant feedback received from the Health Authorities and participating center's Ethics Committees upon review of the protocol. In addition, study population inclusion criteria was expanded, clarifications and corrections are made throughout the protocol, as well as editorial change to improve flow and consistency.

Changes to the protocol

Changes to specific sections of the protocol are shown in the track changes version of the protocol using strike through red font for deletions and red underline for insertions

- Protocol Summary Section updated to match the body of the protocol
- List of Abbreviations was updated
- Section 3 - Study Design: Treatment Period was clarified:
 - One study month is equal to 4 weeks or 28 days.
- Section 5.1 - Inclusion Criteria

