### 5.5.2 Statistical hypothesis, model and method of analysis

The primary analysis will be based on the calculation of the observed pyrexia event rate up to 12 months of therapy (primary endpoint) using the FAS. The observed pyrexia event rate will be summarized using descriptive statistics (N, %) along with its two-sided exact 95% confidence interval (Clopper and Pearson 1934).

In the COMBI-AD study, 87 out of 435 subjects in the treatment arm (20%) developed either grade 3/4 pyrexia or hospitalization due to pyrexia or discontinued due to pyrexia. This rate of 20% will be used as the historical control rate for the assessment of pyrexia management algorithm in this study.

Evidence of treatment effect (improvement in pyrexia event rate using the AE-management algorithm) will be concluded, if the upper bound of the two-sided 95% confidence interval is less than 20%.

The exact 95% confidence intervals for various observed event rates at the primary analysis are shown in [Table 2-5](#). This table has been updated from the protocol for the new sample size = 556 subjects.

If 92 (16.5%) out of 556 subjects are observed with pyrexia event, then the upper bound of the 95% confidence interval will be less than 20%.

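### The interim futility table for the primary endpoint gives the chance of a final rate of 20% or more, but not the chance of meeting the primary objective, which is already about 7% at an interim rate of 20%

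*Protocol*

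**What the plan says.** **Success rule.** Protocol 12.4.2 concludes an effect "if the upper bound of the two-sided 95% confidence interval is less than 20" per cent, using the exact Clopper-Pearson interval. The Protocol summary has the same rule: "The study will meet its primary objective if the upper bound of the two-sided 95% CI is less than 20" per cent. Table 12-1 puts the boundary at 100 events: "If 100 (16.7%) out of 600 subjects are observed with pyrexia event", the upper bound is below 20%, and at 101 it is not. SAP 5.5.2 repeats the rule for the achieved sample: "If 92 (16.5%) out of 556 subjects are observed with pyrexia event", the rule is met.

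**Interim.** Protocol 12.7 plans one futility analysis when "approximately the first 200 subjects dosed have been followed for 6 months". Futility of the primary endpoint rests on the Bayesian "predictive probabilities of the event that observed pyrexia event rate will be 20% or more in the FAS". Table 12-3 tabulates this probability "in the safety set at primary analysis (600 subjects) under different interim results", and the DMC receives it as a criterion that may prompt it to consider stopping in the light of all the data. Two examples are given. At 22% the probability exceeds 80% and stopping might be sensible. The other begins "If the observed pyrexia event rate is 18% at IA" and reports a probability below 20%.

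**Operating characteristics.** Protocol 12.8 with Table 12-5, and SAP section 6 with Table 2-8, count an observed final rate below 20% as success at the primary analysis.

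**The concern.** The plan uses two different final outcomes. The objective requires at most 100/600; the futility statistic asks about 120/600 or more. A final count of 101 to 119 fails the objective but does not add to the futility probability. In the middle of Table 12-3 this band carries a large share of the predictive distribution, so one minus the tabulated figure is not the chance of success. Section 12.8 invites exactly that misreading by equating a rate below 20% with success.

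At stake is what a DMC can learn from the table. The 18% example looks reassuring, and 0.50 at an interim rate of 20% looks like an even chance. Neither describes the prospect of meeting the primary objective. Correcting the success column of Table 12-5 alone would leave the DMC's table as it is.

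**Working it through.** **Inputs.** Prior Beta(0.25, 1), interim n = 200 and final N = 600, so m = 400 future subjects (Protocol 12.7, Table 12-3). Success rule from 12.4.2. N = 556 from the SAP, so m = 356. As in 12.7, the 6-month interim rate is treated as the 12-month rate.

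**Success boundary.** Exact upper bounds are 19.89% for 100/600, 20.07% for 101/600, 19.90% for 92/556 and 20.09% for 93/556. Success therefore means at most 100/600 or at most 92/556, as both documents say.

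**Predictive distribution.** With x interim events, the number Y of later events is beta-binomial with m = 400, a = 0.25 + x and b = 1 + 200 − x.

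- Plan's statistic: P(x + Y ≥ 120)
- Chance of meeting the objective: P(x + Y ≤ 100)
- Band that does neither: P(101 ≤ x + Y ≤ 119)

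**Reproducing the plan.** The first formula returns the entries of Table 12-3, for example 0.1913 at 36, 0.5000 at 40 and 0.8058 at 44.

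**Both probabilities side by side (N = 600).**

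| Interim events /200 | P(final rate ≥ 20%) | P(101–119) | P(meets CI rule) |
|---|---|---|---|
| 30 (15%) | 0.0135 | 0.183 | 0.804 |
| 34 (17%) | 0.0943 | 0.437 | 0.468 |
| 36 (18%) | 0.1913 | 0.514 | 0.294 |
| 38 (19%) | 0.3318 | 0.509 | 0.159 |
| 40 (20%) | 0.5000 | 0.427 | 0.073 |
| 42 (21%) | 0.6673 | 0.304 | 0.028 |
| 43 (21.5%) | 0.741 | 0.242 | 0.016 |
| 44 (22%) | 0.8058 | 0.185 | 0.009 |

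The row for 43 is not in Table 12-3; it comes from the same formula. For N = 556 the chance of meeting the rule at 40/200 is 0.061. At 36/200 the chance of missing the objective is 1 − 0.294 = 0.706, against the 0.19 shown.

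**Sensitivity.** Priors Beta(1,1), Beta(0.5,0.5), Beta(0.2,0.8), Beta(1,4) and the flat limit give 0.061 to 0.073 at 40/200. If success were judged by the supplementary posterior probability of at least 0.95 (at most 104/600, Table 12-2), the figure would be 0.128. Further first events in months 6 to 12 would lower the chance of success.

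**Effect of acting on the added figure.** Stopping at 44/200 or more reproduces the stopping column of Table 12-5 (0.265 at a true 20%). Compare this with stopping when P(meets CI rule) is below 10%, which means 40/200 or more:

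| True rate | Stop at ≥44 | Stop at ≥40 | Overall success, ≥44 | Overall success, ≥40 |
|---|---|---|---|---|
| 15% | 0.5% | 3.4% | 0.883 | 0.869 |
| 17% | 4.0% | 15.0% | 0.438 | 0.425 |
| 20% | 26.5% | 52.8% | 0.021 | 0.020 |

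Overall success here means continuing past the interim and ending with at most 100/600.

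**The case against.** The strongest reply is that this is a stated design choice. Section 12.7 explains that a rate of at least 20% may signal no improvement over the historical control. On that view futility means no better than control, and a lenient screen of that kind is defensible. Table 12-3 says exactly what it tabulates, and Table 12-1 gives the 100/600 boundary to anyone who looks. A trial ending between 17% and 20% would still inform the secondary objectives.

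This largely stands as a defence of keeping the statistic. It does not cover the omission. Section 12.7 presents the statistic as futility of the primary endpoint, and 12.8 calls a rate below 20% study success, which contradicts 12.4.2. A DMC reading both sections has reason to treat the two events as one.

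Stronger readings are tempting but not supported:

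- **The DMC was given a wrong number.** It was not: the figures reproduce and are correctly labelled.
- **A stopping rule lets hopeless trials continue.** No 80% trigger is written as a rule. It can be inferred from Table 12-5, but the text leaves the decision to DMC judgement on all the data. Nor are the prospects hopeless across the range: the chance of success is 0.80 at 30/200 and 0.29 at 36/200.
- **The futility definition should be replaced.** That is a trade-off, since more trials of a truly better algorithm would stop early.
- **The recommendation to continue was mistaken.** The SAP reports that the interim was held with 203 subjects and continuation was advised. It gives no interim count, and the interim SAP and DMC charter it cites are not available here. They may already contain the missing probability.

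The practical consequence is also limited. Enrolment was not to pause, about 570 subjects were expected by the interim cut-off, and subjects still benefiting could continue treatment through a sponsor programme after a futility stop.

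**Conclusion.** The concern holds as a gap in what the interim table shows and as an inconsistency between 12.8 and 12.4.2. The futility statistic and the success rule refer to different final counts, and 101 to 119 of 600 falls between them. The difference is material: 0.19 against a 0.29 chance of success at 36/200, 0.33 against 0.16 at 38/200, 0.50 against 0.073 at 40/200, and 0.74 against 0.016 at 43/200. The prospect of success is very low only from about 40/200 upwards.

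These figures rest on the plan's beta-binomial model, its prior, and equal 6-month and 12-month rates. They do not touch the validity of the final success rule, and they do not show what the DMC actually saw. The change should be made, but it does not undermine the primary analysis.

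**What to change.** 1. Keep the existing column of Table 12-3 and add the predictive probability of meeting the stated success rule (at most 100/600, or at most 92/556 for the achieved sample).
2. Quote it in the 18% and 22% illustrations: 0.29 and 0.009 for N = 600.
3. State in 12.7 and 12.8, and in SAP section 6, that a final rate below 20% is not by itself success.
4. Check whether the interim SAP and DMC charter already gave this probability. Report it for the observed interim count (203 subjects) when the recommendation to continue is interpreted.

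The cost is one column from a formula already in the protocol, plus wording. No new trigger is imposed. The downside arises only if a DMC acts on the added figure. With a cut at 10% (40/200 or more), early stopping would rise from 0.5% to 3.4% at a true rate of 15% and from 4.0% to 15.0% at 17%, and overall success would fall by about 1.4 points in each case (0.883 to 0.869 and 0.438 to 0.425).
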